## 8.1. Efficacy Assessments

## 8.1.1. Participant Diary

Participants will be provided an electronic handheld device or will use their own device to record daily COVID-19 signs and symptoms, study intervention administration, and PRO assessments in the study diary.

Participants will receive daily reminders to complete entries on their own as specified in the SoA. The diary should be completed at approximately the same time every day. Staff will review the participant's study diary online as specified in the SoA.

The diary allows recording of these assessments only within a fixed time window (eg, 24h), thus providing an accurate representation of the participant's experience at that time. The participant is able to make revisions to incorrect entries before pressing the save or submit button. In the event that a participant becomes aware of an error in data after the entry is saved, a change to the diary data may only be made by the investigator submitting a data clarification form. Data reported in the participant diary will be transferred electronically to a third-party vendor, where they will be available for review by investigators and the sponsor or delegate at all times via an internet-based portal.

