### 9.2. Analysis Sets

Participant Analysis Set	Description
Full Analysis Set (FAS)	All participants randomly assigned to study intervention.
Safety Analysis Set	All participants randomly assigned to study intervention
(SAS)	and who take at least 1 dose of study intervention.
	Participants will be analyzed according to the study
	intervention they received.
Modified Intent-To-Treat	All participants randomly assigned to study intervention,
(mITT)	who take at least 1 dose of study intervention, with at least
	1 postbaseline visit through Day 28, who at baseline did
	not receive nor were expected to receive COVID-19
	therapeutic mAb treatment, and were treated $\leq 3$ days after
	COVID-19 symptom onset. Participants will be analyzed
	according to the study intervention to which they were
	randomized.
Modified Intent-To-	All participants randomly assigned to study intervention,
Treat1 (mITT1)	who take at least 1 dose of study intervention, with at least
	1 postbaseline visit through Day 28 and who at baseline
	did not receive nor were expected to receive COVID-19
	therapeutic mAb treatment. Participants will be analyzed
	according to the study intervention to which they were
	randomized.
Modified Intent-To-	All participants randomly assigned to study intervention,
Treat2 (mITT2)	who take at least 1 dose of study intervention, and with at
	least 1 postbaseline visit through Day 28. Participants will
	be analyzed according to the study intervention to which
	they were randomized.
Per-Protocol (PP)	All participants in the mITT set without important protocol
	deviations considered to impact the interpretation of the
	primary efficacy endpoint. Protocol deviations will be
	reviewed to generate the list of participants with significant
	deviations to be excluded from the PP analysis set. The PP

For purposes of analysis, the following analysis sets are defined:

Participant Analysis Set	Description
	exclusion criteria will be finalized prior to breaking the
	blind.

For the primary efficacy analysis, the mITT set will be used and will be the primary analysis. A secondary analysis of the primary endpoint will be performed and will use the mITT2 analysis set. For all other efficacy analyses, mITT, mITT1 and mITT2 sets will be used, as defined in the SAP. The PP analysis set will be used in the analyses of primary efficacy endpoint. The Safety Analysis Set will be used in the analyses of the safety data.

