4. ANALYSIS SETS (POPULATIONS FOR ANALYSIS)

Data for all participants will be assessed to determine if participants meet the criteria for inclusion in each analysis population prior to unblinding and releasing the database and classifications will be documented per standard operating procedures.

Population	Description
Full Analysis Set (FAS)	All participants randomly assigned to study intervention regardless of whether or not study intervention was administered.
Safety Analysis Set (SAS)	All participants who receive at least 1 dose of study intervention. Participants will be analyzed according to the intervention they actually received. A randomized but not treated participant will be excluded from the safety analyses.
Modified Intent-To-Treat (mITT)	All participants randomly assigned to study intervention, who take at least 1 dose of study intervention, who at baseline did not receive nor were expected to receive COVID-19 therapeutic mAb treatment and were treated ≤3 days of COVID-19 onset. Participants will be analyzed according to the study intervention to which they were randomized.
Modified Intent-To-Treat 1 (mITT1)	All participants randomly assigned to study intervention, who take at least 1 dose of study intervention, and who at baseline

Population	Description
	did not receive nor were expected to receive COVID-19 therapeutic mAb treatment. Participants will be analyzed according to the study intervention to which they were randomized.
Modified Intent-To-Treat 2 (mITT2)	All participants randomly assigned to study intervention, who take at least 1 dose of study intervention. Participants will be analyzed according to the study intervention to which they were randomized.
Per-Protocol (PP)	All participants in the mITT set without important protocol deviations considered to impact the interpretation of the primary efficacy endpoint. Protocol deviations will be reviewed to generate the list of participants with significant deviations to be excluded from the PP analysis set. The PP exclusion criteria will be finalized prior to breaking the blind.

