5.3. Methods to Manage Missing Data

For missing efficacy data other than time to event endpoints, a mixed baseline observation carried forward (BOCF)/ last observation carried forward (LOCF) approach will be used. See below:

• For efficacy endpoints related to COVID-19 targeted sign/symptoms, missing data at baseline will be treated as mild. If participant discontinues study due to AE or discontinues study at same time of treatment discontinuation due to lack of efficacy, missing data will use BOCF. Otherwise, missing data will use LOCF.

For safety data, missing and partial dates will be programmatically handled according to Pfizer standards.

PFIZER CONFIDENTIAL
Page 20

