Participants who are hospitalized for the treatment of COVID-19 or death from any cause during the 28-day period will be classified as not achieving sustained symptom alleviation/resolution and will be censored at day 25.

Cox proportional hazard model analyses will be used for time to sustained symptom alleviation/resolution. Cox proportional hazard model will include treatment and region effect as independent variables. In addition, the stratification variables specified in Section 3.5 will be added to the model analyses depending of the analysis population.

Time to sustained symptom alleviation/resolution will be summarized graphically using Kaplan-Meier plots for each of the treatment groups, the analyses will be done using the mITT population only.

In the mITT populations, the analysis will be repeated in subgroups based on baseline serology status (positive, negative), by baseline viral load ($<10^4$ copies/mL, $\ge 10^4$ copies/mL), and ($<10^7$ copies/mL, $\ge 10^7$ copies/mL).

6.2.5. Proportion of Participants with Severe Signs/Symptoms Attributed to COVID-19 through Day 28

Participants will record a daily severity rating of their symptom severity over the past 24 hours based on a 4-point scale in which 0 is reported if no symptoms were present; 1 if mild; 2 if moderate; and 3 if severe.

Vomiting and diarrhea will each be rated on a 4-point frequency scale where 0 is reported for no occurrence, 1 for 1 to 2 times, 2 for 3 to 4 times, and 3 for 5 or greater. Sense of smell and sense of taste will each be rated on a 3-point Likert scale where 0 is reported if the sense of smell/taste was the same as usual, 1 if the sense of smell/taste was less than usual, and 2 for no sense of smell/taste.

The proportion of participants with any severe targeted signs/symptoms attributed to COVID-19 through Day 28 will be summarized by treatment group. A participant with severe score for any targeted symptoms post-baseline will be counted as severe. Proportions for each targeted signs and symptom with severe category only will be plotted over time through Day 28. Additionally, the proportion of participants reporting the presence of each targeted sign and symptom that is mild, moderate or severe categories will also be presented. In addition, to understand the severity of signs/symptoms attributed to COVId-19, the following analysis will be performed:

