- 1. Proportion of participants with any severe targeted signs/symptoms attributed to COVID-19 at DAY 1 (baseline).
- 2. Proportion of participants with any severe targeted signs/symptoms attributed to COVID-19 Day 2 to Day 6 (during treatment).
- 3. Proportion of participants with any severe targeted signs/symptoms attributed to COVID-19 Day 7 to Day 28 (post treatment).

Treatment comparison between the group will be presented as odds ratio and 95% CI using logistic regression with a similar analysis model as specified in Section 6.1.1.2. The analyses will be done using mITT, mITT1, and mITT2 populations.

In the mITT population, the analysis will be repeated in subgroups based on baseline serology status (positive, negative), by baseline viral load ($<10^4$ copies/mL, $\ge10^4$ copies/mL) and ($<10^7$ copies/mL, $\ge10^7$ copies/mL).

An additional follow-up analysis for signs/symptoms data will be conducted at Week 12 and Week 24 for all signs/symptoms (not just targeted signs/symptoms, See Appendix 5). The Week 12 and Week 24 signs/symptoms data is collected from a long-term FU telemedicine interview performed by the site to participant and collected in CRF (diary data is not colected after Day 34).

The observed proportion of participants with any mild, moderate, and severe of all signs/symptoms attributed to COVID-19 at Week 12 and Week 24 will be summarized by treatment group and overall. Observed proportion of participants reporting the presence of each sign and symptom that is mild, moderate, or severe categories will also be summarized by treatment group and overall.

The analyses will be done using mITT, mITT1, and mITT2 populations.

6.2.6. Duration of Each Targeted COVID-19 Sign/Symptom through Day 28

Duration of each targeted COVID -19 signs/symptoms is defined as (First Date when the symptom alleviated/resolved) – (First Dose Date) +1 for each participant with baseline severity of mild, moderate or severe.

PFIZER CONFIDENTIAL
Page 25

Duration of each targeted COVID-19 sign/symptom with a mild or worse severity will be summarized for each group within mITT, mITT1, and mITT2 populations.

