For duration of each targeted COVID19 sign/symptom, a Kaplan-Meier analysis providing the median and quartiles will be provided for each treatment group for mITT population set. Two additional figures (Number of Participants and Median Time to Sustained Alleviation of Each Targeted Sign/Symptom by Treatment Group [mITT) will be included for the endpoint of Duration of Each Targeted COVID-19 Sign/Symptom.

6.2.7. Progression to a Worsening Status in 1 or More Self-reported COVID-19 Associated Symptoms through Day 28

Participants will record a daily severity rating of their symptom severity over the past 24 hours based on a 4-point scale in which 0 is reported if no symptoms were present; 1 if mild; 2 if moderate; and 3 if severe. Vomiting and diarrhea will each be rated on a 4-point frequency scale where 0 is reported for no occurrence, 1(mild) for 1 to 2 times, 2 (moderate) for 3 to 4 times, and 3 (severe) for 5 or greater.

Progression to a worsening status for any targeted symptom will be derived programmatically based upon increasing severity (ie, the first time any targeted symptoms worsen after treatment relative to baseline):

Progression to worsening (Yes/No)	
Increasing severity	Yes
Not increasing severity	No

The proportion of participants with progression (increasing severity for any targeted symptom) will be summarized by treatment group. Treatment comparison between groups will be presented as odds ratios with 95% confidence intervals and P-value based on logistic regression model as specified in Section 6.1.1.2. The analyses will be done using mITT, mITT1, and mITT2 population. Missing severity at baseline will be treated as mild.

6.2.8. Proportion of Participants with a Resting Peripheral Oxygen Saturation ≥95% at Days 1 and 5

The oxygen saturation level will be measured for each participant. A resting peripheral oxygen saturation will be derived programmatically based on the following table:

Oxygen saturation (Yes/No)	
≥95%	Yes
<95%	No

PFIZER CONFIDENTIAI	
Page 26	

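### For the any-severe-symptom analyses (SAP 6.2.5), BOCF/LOCF can add events only by copying an old severe score across a window border, even after one missed diary day

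*SAP*

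**What the plan says.** **Imputation rule.** SAP 5.3 covers missing efficacy data other than time-to-event endpoints. For targeted symptoms, a missing baseline score is set to mild. The baseline score is carried forward after study discontinuation for an adverse event, or when a participant "discontinues study at same time of treatment discontinuation due to lack of efficacy, missing data will use BOCF. Otherwise, missing data will use LOCF". No gap length is stated, and intermittent missed days are not mentioned. The Appendix 1 row for severe signs/symptoms through Day 28 repeats BOCF/LOCF.

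**Endpoint.** SAP 6.2.5 states: "A participant with severe score for any targeted symptoms post-baseline will be counted as severe". It adds three separate proportions: Day 1 (baseline), Day 2-6 (during treatment), and a last one for "any severe targeted signs/symptoms attributed to COVID-19 Day 7 to Day 28 (post treatment".

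**Data source.** Protocol 8.1.1 says: "The diary allows recording of these assessments only within a fixed time window (eg, 24h". The later-change route there is for errors in saved entries, so a missed day normally stays missing.

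**Population.** The SAP Section 4 mITT definition takes participants "who take at least 1 dose of study intervention, who at baseline did not receive" mAb treatment and were not expected to. Protocol 9.2 also asks for at least "1 postbaseline visit through Day 28".

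**Method.** SAP 6.2.5 uses logistic regression, and the version history records that it replaced Kaplan-Meier. Appendix 1 still lists both for this row, and SAP 5.2.1 still describes a difference in proportions.

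**The concern.** The three windows exist to separate severity at baseline, on treatment and after treatment. For an endpoint of the any-severe-score type, one imputed severe day decides a participant's status, and carry-forward can move a score across exactly those borders. The Day 7-28 proportion can then include people whose only severe scores were recorded on treatment or at baseline. The through-Day-28 proportion can include people whose only severe score was at baseline.

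At stake is the reading of a secondary severity endpoint, which SAP 6.2.5 analyses in three populations and in mITT subgroups. No analysis restricted to recorded scores is planned beside it.

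**Working it through.** The plan states no figure for this, so the check is first one of logic and then an illustration of size.

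**1. What carry-forward can add.** A missing baseline becomes mild, so it cannot create a severe score. Every other imputed score copies a recorded one, and recorded scores are never overwritten. Hence an imputed severe score always has an earlier recorded source, and no recorded event is lost.

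This was confirmed on a shortened diary of baseline plus six days in two windows, with each entry severe, not severe or missing:

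- 3^7 = 2,187 patterns × 2 rules × 3 windows = 13,122 checks.
- Events added without an earlier recorded severe score: 0.
- Recorded events removed: 0.

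**2. When LOCF adds an event.** The first day of the window must be missing and the last recorded score before it must be severe. An isolated gap later in the window only repeats an in-window score and adds nothing.

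| Analysis | Route by which an event is added |
|---|---|
| Post-baseline through Day 28 | Severe baseline with Day 2 missed, or no post-baseline entry at all |
| Day 2-6 | Severe baseline with Day 2 missed |
| Day 7-28 | Last score before Day 7 severe, and Day 7 missed |

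In each case the participant has no recorded severe score in that window. BOCF adds a further route: a severe baseline placed after discontinuation, even if the participant had improved by then.

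**3. Worked diary.** Severe on Days 2 to 6, Day 7 missed, mild on Days 8 to 28. Recorded scores show nothing severe in Day 7-28. LOCF makes Day 7 severe, so the participant counts as a post-treatment event.

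**4. Illustrative size for Day 7-28 under LOCF.** All three inputs are assumptions; none is in the documents.

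- q = share of an arm whose last entry before Day 7 is severe, 5-20%.
- m = share of those missing Day 7, whether they resume or not, 5-20%.
- r = share of those with no severe score recorded in Day 7-28, 50-80%. For anyone who never resumes the diary it is 100%, so r is an average over both kinds.

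Added events as a share of the arm = q × m × r. Per arm, mITT has about 1717/2 ≈ 858 participants.

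| Case | q × m × r | Points | Of 858 |
|---|---|---|---|
| Low | 0.05 × 0.05 × 0.50 | 0.125 | about 1 |
| Middle | 0.10 × 0.10 × 0.50 | 0.5 | about 4 |
| High | 0.20 × 0.20 × 0.80 | 3.2 | about 27 |

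A second set of assumptions (q 5-15%, m 5-20%, r 30-90%) gives 0.05 × 0.05 × 0.30 = 0.075 to 0.15 × 0.20 × 0.90 = 2.7 points. The high cases put every input at its upper limit. The BOCF route is not included.

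**5. Direction.** The shift in placebo minus active is m × (qP × rP − qA × rA). With m = 10%:

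- q 15% against 10%, r 50% in both arms: 0.1 × (0.075 − 0.050) = +0.25 points.
- q 12% against 10%, r 50% against 80%: 0.1 × (0.060 − 0.080) = −0.20 points.

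A better arm has fewer severe scores to carry, but more of those carried lack a later recorded severe score because its symptoms clear sooner.

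**The case against.** **The rule may be narrower than its wording.** In SAP 5.3 the word *otherwise* follows a sentence about people who leave the study, so it may have meant only other discontinuations. The Appendix 1 row names only the through-Day-28 proportion, and the window analyses are reached only through the general rule. This stands as a possible intention. The text does not state it, however, and even the narrow reading carries a severe score or a severe baseline into Day 7-28 after an exit.

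**The added events may be real.** Day 7 is unobserved, and someone severe on Day 6 may well be severe on Day 7. Counting recorded scores only treats that day as not severe, which is also an assumption and the more favourable one. This stands: the added events are unsupported, not shown to be wrong.

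**Exclusion has a price.** Dropping participants with no in-window score selects on post-randomization data. This stands, and it is why the carried-forward result should be kept alongside.

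A reader might also infer more than the documents support:

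- *That the analysis-set change is itself a fault.* The version history says V1.4 made it at FDA request. Its only consequence here is that a participant without any post-baseline entry is classified from baseline.
- *That the worsening endpoint (SAP 6.2.7) has the same problem.* It counts "the first time any targeted symptoms worsen after treatment relative to baseline". A copied score is either the baseline itself or one already counted, so carry-forward adds no event.
- *That hospitalized or deceased participants are misclassified.* SAP 6.2.4 says they "will be classified as not achieving sustained symptom alleviation/resolution and will be censored at day 25", but that endpoint measures recovery. Here the definition rests on diary scores, and Protocol Section 8 continues assessments in hospital as feasible. A composite would be a different endpoint.
- *That the SAP already sets a precedent by not imputing symptom duration.* SAP 5.2.5 treats duration as time-to-event, which 5.3 exempts.

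**Conclusion.** The point holds and is minor. On the plain text, a severe score can be counted in a window in which none was recorded, after as little as one missed day at the window's start. That blurs the separation for which the window analyses were added.

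The size is unknown and probably small: about 0.1 to 3 points per arm, resting wholly on assumed shares. The documents do not support reading this as a bias towards or against the active arm, since the illustrations go both ways. Nor do they support carrying it over to the main conclusions. The primary endpoint does not use this rule, and the endpoint is not among the tests listed in SAP 5.1. Protocol 9.1 sends other secondary endpoints to Hochberg without naming them, so the SAP list is the one relied on here.

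The Kaplan-Meier and difference-in-proportions wording is an editorial leftover, because SAP 6.2.5 and the version history already settle on logistic regression.

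**What to change.** 1. In SAP 5.3, 6.2.5 and the Appendix 1 severe-symptom row, state that for any-severe a baseline score is never carried into the post-baseline period, and no score is carried from one window into the next. Count only severe scores recorded in the window analysed: post-baseline through Day 28, Day 2-6, or Day 7-28.
2. Report by arm how many participants have no recorded score in each window.
3. Keep the BOCF/LOCF version as a reported sensitivity analysis, which also covers participants who leave the comparison. For that version, say whether LOCF applies to intermittent missed days or only after discontinuation.
4. Delete the leftover Kaplan-Meier entry in that Appendix 1 row, and align SAP 5.2.1 with the logistic regression in 6.2.5.

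The cost is SAP wording and a little programming. Some participants will have no in-window score and drop out of that comparison. The change would follow an interim analysis whose objective the version history records as met, so it should be dated and the reason given.

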6. ANALYSES AND SUMMARIES

6.1. Primary Endpoint

6.1.1. Primary Endpoint/Estimand Analysis

6.1.1.1. Main Analysis

The primary endpoint is proportion of participants with COVID-19 related hospitalization or death from any cause through Day 28 in the mITT population. The cumulative proportion of participants hospitalized for the treatment of COVID-19 or death during the first 28 days of the study will be estimated for each treatment group using the Kaplan-Meier method to take account of losses to follow-up and summarized graphically for each treatment group.

The estimand is then the difference of the proportions in the 2 treatment groups and its 95% confidence interval will be presented, as well as, the associated two-sample proportion test. For the 95% CI, the corresponding estimate of the standard error is computed using Greenwood's formula (Kalbfleisch and Prentice; 1980). The Greenwood's formula to estimate the variance of the difference of proportions at Day 28 is $[Var(S_{PF}(28)) + Var(S_{Placebo}(28))]$. Instead of dealing with $S(t_i)$ we will use the log-log approach to CI. The 95% CI will be computed for the estimate of L(t) = log(-log(S(t))), the log hazard function.

$$Var(\hat{L}(t)) = Var[log(-log(\hat{S}(t)))]$$

The CI will be in right range when we transform back to $S(t) = \exp(-\exp(L(t)))$. Antilogging this confidence interval will give a 95% confidence interval for the difference itself.

The above primary analysis will be conducted for the planned interim analyses as well. Two-sided 95% CI (adjusted for the planned interim analyses) and associated p-value (two-sample proportion test) for the null hypothesis of no difference between treatment groups will be presented. Significance level will be determined using the O'Brien-Fleming approach at the interim analysis and the final analysis. The overall significance level is set at 5% (2 sided).

For participants who complete Day 28 efficacy assessment (Day 34 visit), they will be censored at their last visits. For participants who discontinue before Day 28 assessment or are lost to follow-up, they will be censored at the last known date in the study.

Participants will be analysed under the mAb stratum assigned at randomization/baseline.

The proportion of participants with COVID-19 related hospitalization or death from any cause through Day 28 will be summarized graphically using Kaplan-Meier plots for each of the treatment groups, the analyses will be done using mITT, mITT1, and mITT2 populations.

The sensitivity analysis associated with primary endpoint will be conducted using the mITT2 population set. Four additional sensitivity analysis for the primary endpoint will be performed:

- a sensitivity analysis excluding all data from India sites for the mITT population;
- a sensitivity analysis excluding all participants from Site 1470 for the mITT, mITT1 and mITT2 populations;
- a sensitivity analysis excluding participants from the sentinel cohort of the study treated with active treatment (3 doses of 100 mg) for the mITT population;
- An additional sensitivity analysis for participants with missing data (i.e., participant who was without any COVID-19 related hospitalization or death of any cause but discontinued from study due to lost to follow up and their last observations are <28 days) will be performed for the mITT population. The sensitivity analysis will implement the following event imputation methodology for those with missing data for primary endpoint:
 - If the participant's last observed data is prior to Day 21, then impute as an event with event day as day of last observed data +1.
 - If the participant's last observed data is on or after Day 21, do not impute an event and participant remains censored at day of last observed data.

